### INTRODUCTION & BACKGROUND

[figure not shown]
Cardiac allograft vasculopathy (CAV) is an important cause of morbidity and mortality among pediatric and adult transplant recipients.(13-15) Due to the often asymptomatic nature of disease progression serial surveillance is recommended for all cardiac transplant recipients, however current techniques are either invasive and/or lack sensitivity to detect early stages of CAV due to its significant effect on coronary microvasculature. Real time myocardial perfusion echocardiography (RTMPE) is a safe and feasible non-invasive technique commonly used to diagnose coronary disease, and offers an attractive alternative for CAV detection.

The incidence of CAV is approximately 10% at 1 year post-transplant, 30% at 5 years and 50% at 10 years, and it has become one of the leading causes of graft loss and death after the first year.(13) CAV is a diffuse and accelerated fibro-proliferative process that affects both the large epicardial and small intramyocardial allograft coronary arteries (Figure 1).(16) Early detection of CAV is critically important because it allows alterations to medical therapy to slow progression before revascularization is required. Early detection is challenged by the often asymptomatic nature of disease progression, making routine CAV screening the current standard of care for transplant recipients. Invasive coronary angiographic (ICA) imaging is the gold standard for the detection of CAV, but is invasive (and may require a general anesthetic in the pediatric population) and exposes the patient to ionizing radiation, while current noninvasive methods best evaluate the large vessels with limitations for the detection of small vessel disease.

[figure not shown]
The objectives of this study are to determine the feasibility and diagnostic accuracy of RTMPE to detect CAV in pediatric and adult transplant recipients. We hypothesize that RTMPE is an effective non-invasive method for CAV detection in these populations, and that perfusion deficits will correlate with significant coronary artery stenosis identified by standard stress echocardiography and invasive angiography.

Real-time myocardial perfusion echocardiography (RTMPE) may offer an attractive alternative to ICA for the detection of CAV.(17-20) RTMPE utilizes the intravenous administration of biologically-inert microbubbles to assess myocardial perfusion,(6) and has demonstrated utility for identifying small vessel coronary artery disease.(7) Although contrast echocardiography has found common application for evaluation of coronary artery disease in adult non-transplant recipients,(6) this safe and potentially useful imaging modality remains understudied in CAV with only two small single center studies published in the current literature (Figure 2).(21,22) The contrast medium administered in RTMPE is routinely used without significant side effects in adults (8,23,24) and has been studied in pediatric populations with no adverse effects.(12) The purpose of this study is to evaluate the feasibility and diagnostic utility of RTMPE for the detection of CAV in adult and pediatric transplant recipients from a multicenter experience

Cardiac transplant recipients followed at Mayo Clinic (Rochester, MN) will be included. The study population will be divided into adult and pediatric subgroups. Consenting patients will undergo rest and pharmacologic stress perfusion RTMPE. Results of RTMPE will be correlated with wall motion assessment by standard stress echocardiography and clinically indicated invasive coronary angiography (including intravascular ultrasound findings when available). We expect that RTMPE will be well tolerated and findings of myocardial perfusions defects will correlate with current CAV surveillance techniques. RTMPE may represent a preferred method and new clinical standard for CAV surveillance among adult and pediatric cardiac transplant recipients.

**Figure 1**. Marked concentric intimal hyperplasia and proliferation associated with cardiac allograft vasculopathy. Pollack et al, JACC CV Img 2013.

**Figure 2**. Myocardial contrast echocardiography from the apical 4-chamber view demonstrating an apical and lateral wall perfusion defect (arrows) during peak dobutamine stress (right) compared with normal perfusion at rest (left). Rodriguez et al, JASE 2005.

### **OBJECTIVES**

- To determine the feasibility of real time myocardial perfusion echocardiography (RTMPE) for the detection of coronary allograft vasculopathy (CAV) in pediatric and adult cardiac transplant recipients.
- To determine the diagnostic accuracy of RTMPE for the detection of CAV in pediatric and adult cardiac transplant recipients compared with current standardized methods.

### **HYPOTHESIS**

RTMPE is a feasible and effective non-invasive method to detect significant CAV in pediatric and adult cardiac transplant recipients. Perfusion deficits will correlate with significant coronary artery stenosis identified by standard stress echocardiography and ICA, and may identify diffuse small vessel disease more effectively than current noninvasive techniques.

### STUDY DESIGN

This will be a prospective, observational cohort study. The study population will be divided into adult (age  $\ge 18$  years-old) and pediatric (age  $\le 18$  years-old) subgroups, each with a separate

recruitment process and data analysis. Eligible subjects will be screened and recruited through the Transplant Clinic. Consenting patients will undergo rest and dobutamine stress RTMPE at in the echocardiography laboratory using a standardized imaging protocol.(8) Relevant clinical data will be collected from the electronic medical records.

Dobutamine stress echocardiograms will be performed per institutional protocol.

For adults, standard dosing of DEFINITY® (Perflutren Lipid Microsphere) Injectible Suspension ultrasound contrast agent will be used. For each adult, the vial of DEFINITY® contrast will be divided in half (~0.75 mL) and drawn up into two 30 mL syringes pre-filled with 29.25 mL of normal saline. Hand injections of the solution will be performed at baseline, prepeak, and peak perfusion stages.

For pediatric patients > 60 kg, the standard adult dosing will be used. For pediatric patients under 60 kg, the dose will be 20 microL/kg diluted to the same concentration used in the adult dosing. Hand injections will be performed at baseline, pre-peak, and peak perfusion stages.

### **INCLUSION CRITERIA**

- Cardiac transplant recipients (≥10 months post transplant)
- Clinically followed at Mayo Clinic (Rochester MN)

### **EXCLUSION CRITERIA**

- Standard contraindications to the use of ultrasound contrast and pharmacologic stress (6,25)
- Recent (<3 months) hospitalization for heart failure, acute coronary syndrome or allograft rejection
- Multi-organ transplant
- Known or suspected right-to-left, bi-directional or transient right-to-left cardiac shunts
- Hypersensitivity to perflutren

### **ENDPOINTS**

The primary study endpoint will be presence of a perfusion defect by RTPME. Results of RTMPE will be correlated with wall motion assessment by standard stress echocardiography (available at the time of RTMPE) and with clinically indicated ICA (including intravascular ultrasound findings when available) performed within 3 months of RTMPE. Pediatric cardiac transplant recipients at Mayo Clinic undergo annual or bi-annual surveillance ICA, while adult

cardiac transplant recipients at Mayo Clinic undergo annual surveillance ICA. Grading of ICA (13) and RTMPE (8) will be performed independently by two experienced reviewers in a blinded fashion. Safety and adverse event data for RTMPE will be collected.

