### SAMPLE SIZE & DATA ANALYSIS

A conservative estimated disease prevalence of 25% among adult transplant recipient and 10% among pediatric transplant recipients is anticipated.(13) For both pediatric and adult patients there are no prior large population studies for estimated diagnostic accuracy of RTMPE for detection of CAV, and so sample size estimates are challenging. A target of 25 adult and 25 pediatric patients for appropriate pilot data will be used. Data will be expressed as the mean  $\pm$  standard deviation for continuous variables, and as absolute frequencies or relative percentages for categorical variables. Comparison between groups (with and without CAV by ICA) for continuous variables will be done using analysis of variance, and for categorical variables using  $\chi_2$  analysis. Comparison of RTMPE with wall motion stress echocardiography and with ICA will be performed using 2x2 contingency tables on a per patient and per coronary artery territory perfusion defect distribution basis. All comparisons of diagnostic accuracy will be made on the basis of binary outcome data analysis of paired within patient data. All p-values will be 2-sided, and a value of  $\leq$  0.05 will be considered statistically significant. Data analysis will be performed using statistical software.

**Safety Statement:** RTMPE utilizes the intravenous administration of chemically- and biologically-inert microbubbles to assess myocardial perfusion, and may demonstrate improved detection of small vessel disease. The ultrasound microbubble contrast medium used in RTMPE is routinely used without significant side effects in adults for other indications. It has been used in children on a case-by-case basis with no recognized safety issues unique to children. However, for the purposes of this study (perfusion), it would be considered off-label for both adults and children.

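### Blinded grading is specified for ICA and RTMPE but not for wall motion, so the paired RTMPE versus wall-motion comparison is open to review bias

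*Combined protocol and SAP*

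**What the plan says.** All documents here are the combined protocol and SAP.

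- **Blinding (ENDPOINTS).** "Grading of ICA (13) and RTMPE (8) will be performed independently by two experienced reviewers in a blinded fashion". What the reviewers are blinded to is not stated.
- **The comparator (ENDPOINTS).** RTMPE is to be correlated with "wall motion assessment by standard stress echocardiography (available at the time of RTMPE") and with clinically indicated ICA. Wall motion does not appear in the blinding sentence.
- **Acquisition (STUDY DESIGN).** "Consenting patients will undergo rest and dobutamine stress RTMPE", and "Dobutamine stress echocardiograms will be performed per institutional protocol". No study-specific reading procedure for wall motion is given.
- **Analysis (SAMPLE SIZE & DATA ANALYSIS).** "Comparison of RTMPE with wall motion stress echocardiography and with ICA will be performed using 2x2 contingency tables", both per patient and per coronary territory. "All comparisons of diagnostic accuracy will be made on the basis of binary outcome data analysis of paired within patient data".
- **What the comparison is for (HYPOTHESIS).** RTMPE "may identify diffuse small vessel disease more effectively than current noninvasive techniques". The lay abstract likewise asks whether it is the better surveillance test.

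**The concern.** A paired comparison of two imaging tests can be interpreted cleanly only if each is read without knowledge of the other. Here three results feed the tables, and only two are declared blinded. Nothing prevents the wall-motion call from being made with the perfusion finding or the angiogram known, and nothing says expressly that the RTMPE reviewers are kept from the wall-motion report.

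Any advantage of RTMPE over wall motion shows only in patients on whom the two tests disagree. Those are the calls most likely to change when a reader knows the other result. The tables could then overstate agreement and understate the difference, and the pilot would pass a distorted estimate to the larger comparative study it is meant to support.

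**Working it through.** **Is the gap closed elsewhere?** Set side by side, the sections give:

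| Result | Reader | Blinded | Blinded to what |
|---|---|---|---|
| ICA | two reviewers | yes | not stated |
| RTMPE | two reviewers | yes | not stated |
| Wall motion | not stated | not stated | not stated |

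No other section names a wall-motion reader, separates that reader from the RTMPE reviewers or sets a reading order. The clear gap is therefore the wall-motion read, and that is the read modelled below.

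**Inputs from the plan.** n = 25 adults ("A target of 25 adult and 25 pediatric patients for appropriate pilot data will be used"), adult CAV prevalence 25%, paired binary data. The plan gives no accuracy or agreement figure to reproduce.

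**Assumed inputs.** RTMPE sensitivity 0.80, specificity 0.85; wall motion 0.50 and 0.85; errors independent given CAV status. A fraction f of the wall-motion calls that would disagree with RTMPE is switched to match it, with f = 0, 0.25 or 0.50.

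**Step 1: discordance without bias.**
- RTMPE positive, wall motion negative: b = 0.25 × 0.80 × 0.50 + 0.75 × 0.15 × 0.85 = 0.1956
- RTMPE negative, wall motion positive: c = 0.25 × 0.20 × 0.50 + 0.75 × 0.85 × 0.15 = 0.1206
- b + c = 0.3163, or 25 × 0.3163 = 7.9 patients.

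**Step 2: apparent wall-motion accuracy.**
- Sensitivity = 0.50 + f × (0.80 × 0.50 − 0.20 × 0.50) = 0.50 + 0.30f, giving 50%, 57.5%, 65%.
- Specificity = 0.85 + f × (0.85 × 0.15 − 0.15 × 0.85) = 85% throughout.
- RTMPE sensitivity stays at 80%, so the difference is 30 × (1 − f) = 30, 22.5, 15 points. This step does not need conditional independence: the gap between the two discordant cells among CAV patients always equals the sensitivity difference.

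**Step 3: kappa.** Observed agreement Po = 1 − (1 − f)(b + c). RTMPE-positive proportion = 0.25 × 0.80 + 0.75 × 0.15 = 0.3125. Wall-motion-positive proportion w = 0.2375 + f(b − c) = 0.2375 + 0.075f. Chance agreement Pe = 0.3125w + 0.6875(1 − w). Kappa = (Po − Pe)/(1 − Pe).

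| f | Po | Pe | Kappa | Expected discordant pairs of 25 | Wall-motion sensitivity | Difference |
|---|---|---|---|---|---|---|
| 0 | 0.684 | 0.598 | 0.21 | 7.9 | 50% | 30 points |
| 0.25 | 0.763 | 0.591 | 0.42 | 5.9 | 57.5% | 22.5 points |
| 0.50 | 0.842 | 0.584 | 0.62 | 4.0 | 65% | 15 points |

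**Step 4: sensitivity to the assumptions.** Three other sets (RTMPE/wall motion, sensitivity and specificity: 80/80 and 60/85; 70/85 and 50/90; 90/80 and 70/80), each at the plan's 25% adult and 10% pediatric prevalence, gave kappa of 0.14 to 0.29 at f = 0 and 0.59 to 0.65 at f = 0.50. In every set the sensitivity difference fell from 20 to 15 and then 10 points.

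**The case against.** **RTMPE is already blinded.** The blinding sentence follows shortly after both comparators are named, so blinding to both is a fair reading. A reader might infer that the plan exposes the RTMPE reviewers to the wall-motion call and that RTMPE sensitivity would fall. The documents do not support that: they say RTMPE grading is blinded and leave only its object unstated. What stands is that the wall-motion read is unprotected on either reading, and one unprotected read is enough to affect a paired table.

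**The direction is not certain.** This is correct. If RTMPE reviewers did know wall motion and merely added its positives, in 50% or 100% of patients positive on wall motion only, RTMPE sensitivity would rise from 80% to 80 + 0.5 × 10 = 85% or 90%. Specificity would fall from 85% to 85 − 0.5 × 12.75 = 79% or 72%, and the sensitivity gap would widen to 35 or 40 points. Convergence is the likely effect, not the only one.

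**Same session is not stated.** The parenthesis on availability, read with STUDY DESIGN, makes one stress session probable, but the plan does not say so. The point does not depend on it.

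**It is a pilot.** A reader might argue that lost discordant pairs cost a significant result, since an exact paired test needs at least 6, all one way (5 give 2 × 0.5^5 = 0.0625; 6 give 2 × 0.5^6 = 0.031). That adds little. The plan names no exact test, and with the inputs above and no bias such a test would reach p ≤ 0.05 in only about 5% of 25-patient samples. The harm is to the estimates.

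**Scope.** The primary endpoint is presence of a perfusion defect, and the ICA comparison has blinded grading on both sides. That comparison is less affected.

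**Conclusion.** The concern holds for the RTMPE versus wall-motion comparison. The plan makes wall motion a formal paired comparator but leaves it out of the blinded gradings, and does not say whether RTMPE blinding covers it. The expected consequence is inflated agreement and a smaller apparent difference. In the illustration, a 30-point sensitivity difference becomes 22.5 or 15 points and kappa of 0.21 becomes about 0.42 or 0.62.

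These sizes rest on assumed accuracies and assumed switching fractions, and kappa also rests on conditional independence. If the two readings share errors, unbiased kappa would be higher and its inflation smaller. The figures show what review bias could do; they are not evidence that it will occur. The plan should be changed before grading starts, because a reading made with the other result known is hard to undo.

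**What to change.** In ENDPOINTS, add wall motion to the blinded gradings and state for each grading what the reviewers are kept from:

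1. The existing reviewers grade wall motion first, without the perfusion grading or ICA, and the result is locked.
2. RTMPE is graded in a later, separate session, in random and de-identified order, without the wall-motion report or ICA.
3. If RTMPE loops unavoidably show wall motion, the plan says so and interprets the comparison as the incremental value of perfusion over wall motion.

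The cost is protocol wording and some extra reading time for 50 studies (25 + 25), with no added procedure for patients. If the same reviewers grade both tests, some recall remains; it should be acknowledged as a limitation.

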### SAMPLE SIZE & DATA ANALYSIS

A conservative estimated disease prevalence of 25% among adult transplant recipient and 10% among pediatric transplant recipients is anticipated.(13) For both pediatric and adult patients there are no prior large population studies for estimated diagnostic accuracy of RTMPE for detection of CAV, and so sample size estimates are challenging. A target of 25 adult and 25 pediatric patients for appropriate pilot data will be used. Data will be expressed as the mean  $\pm$  standard deviation for continuous variables, and as absolute frequencies or relative percentages for categorical variables. Comparison between groups (with and without CAV by ICA) for continuous variables will be done using analysis of variance, and for categorical variables using  $\chi_2$  analysis. Comparison of RTMPE with wall motion stress echocardiography and with ICA will be performed using 2x2 contingency tables on a per patient and per coronary artery territory perfusion defect distribution basis. All comparisons of diagnostic accuracy will be made on the basis of binary outcome data analysis of paired within patient data. All p-values will be 2-sided, and a value of  $\leq$  0.05 will be considered statistically significant. Data analysis will be performed using statistical software.

**Safety Statement:** RTMPE utilizes the intravenous administration of chemically- and biologically-inert microbubbles to assess myocardial perfusion, and may demonstrate improved detection of small vessel disease. The ultrasound microbubble contrast medium used in RTMPE is routinely used without significant side effects in adults for other indications. It has been used in children on a case-by-case basis with no recognized safety issues unique to children. However, for the purposes of this study (perfusion), it would be considered off-label for both adults and children.

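### With the 2–3 pediatric and about 6 adult CAV cases the plan expects, chi-square p-values for CAV versus no-CAV comparisons are unreliable; an exact test should be named instead

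*Combined protocol and SAP*

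**What the plan says.** All references are to the combined protocol and SAP.

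- **Sample Size & Data Analysis, tests.** "Comparison between groups (with and without CAV by ICA) for continuous variables will be done using analysis of variance, and for categorical variables using" chi-square. Tests are two-sided, and p at or below 0.05 counts as significant. No exact test, continuity correction, small-cell rule or unequal-variance alternative is named, and the software is not identified.
- **Same section, size.** "A target of 25 adult and 25 pediatric patients for appropriate pilot data will be used". No power or precision calculation supports this; the text says "so sample size estimates are challenging".
- **Same section, prevalence.** "A conservative estimated disease prevalence of 25% among adult transplant recipient and 10% among pediatric transplant recipients is anticipated".
- **Study Design.** Each age group has its own "recruitment process and data analysis", so CAV cases are not pooled across adults and children.
- **Endpoints.** CAV status comes from clinically indicated angiography within 3 months of the study echocardiogram, so fewer than 25 patients per group may be classifiable.

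**The concern.** The chi-square p-value rests on a large-sample approximation that is usually trusted only when expected cell counts reach about 5. The plan never states its expected number of CAV cases, but its own inputs fix it, and it is far too small for that approximation. Analysis of variance adds a second exposure. It assumes one common variance, and when one group is tiny the result depends heavily on whether that is true.

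At stake is which patient characteristics the pilot reports as significantly associated with CAV. The section on impact and future research says the data will support a larger multicenter study. A very small p-value produced by a single child could influence that design more than the evidence warrants.

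**Working it through.** **Inputs.** 25 patients per age group and prevalences of 25% (adults) and 10% (children), from Sample Size & Data Analysis; separate analysis by age, from Study Design. The 25 + 25 target comes from no formula, so there is no planned figure to reproduce.

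**1. Expected cases.** Adults 25 x 0.25 = 6.25; children 25 x 0.10 = 2.5. In children the binomial chance of no case is 0.9^25 = 7.2%, of at most one case 27.1%, and of fewer than five 90%.

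**2. Expected cells.** With m CAV cases among 25 and k patients positive on a binary variable, the CAV-row expected counts are mk/25 and m(25 − k)/25. The smaller of k and 25 − k is at most 12, so the smallest expected cell is at most 12m/25: 0.96 for m = 2, 1.44 for m = 3 and 2.88 for m = 6. Reaching 5 needs m of at least 5 x 25/12 = 10.4, that is 11 cases. No 2x2 table at the expected case counts qualifies.

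**3. Individual tables.** Uncorrected chi-square = N(ad − bc)² / (product of the four margins).

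- 1/2 v 0/23: 25 x 23² / (2 x 23 x 1 x 24) = 11.98
- 1/3 v 0/22: 25 x 22² / (3 x 22 x 1 x 24) = 7.64
- 3/6 v 2/19: 25 x 45² / (6 x 19 x 5 x 20) = 4.44
- 1/6 v 0/19: 25 x 19² / (6 x 19 x 1 x 24) = 3.30

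| Table (CAV v no CAV) | Chi-square p | Yates p | Fisher p | Boschloo p |
|---|---|---|---|---|
| Children 1/2 v 0/23 | 0.0005 | 0.11 | 0.080 | 0.064 |
| Children 1/3 v 0/22 | 0.006 | 0.23 | 0.12 | 0.10 |
| Adults 3/6 v 2/19 | 0.035 | – | 0.070 | 0.071 |
| Adults 1/6 v 0/19 | 0.069 | 0.53 | 0.24 | – |

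The Fisher values in the first two rows can be read directly. If exactly one child of 25 is positive, the chance that this child is a CAV case is 2/25 = 0.08 or 3/25 = 0.12. Chi-square reports that event as p = 0.0005 or 0.006.

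**4. Error rate at 0.05.** Every 2x2 table was enumerated over common event rates from 0.005 to 0.995. The worst-case error of uncorrected chi-square is 7.2% (2 v 23), 5.1% (3 v 22) and 6.0% (6 v 19).

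**5. Continuous variables.** Simulated error at nominal 5% with normal data. The SD ratios (CAV group to the rest) are assumptions; the documents give none.

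| SD ratio | 2 v 23 | 3 v 22 | 6 v 19 |
|---|---|---|---|
| Analysis of variance, 1 | 5.0% | 4.9% | 5.1% |
| Analysis of variance, 1.5 | 16% | 15% | 11% |
| Analysis of variance, 2 | 27% | 24% | 16% |
| Analysis of variance, 0.5 | 0.2% | 0.3% | 0.9% |
| Welch, 1 to 2 | about 12% | 7–8% | about 5.4% |

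With lognormal data of the same shape in both groups, analysis of variance gives 6.4%, 6.0% and 4.5%.

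**6. Mid-p as a remedy.** Fisher's mid-p gives 0.040 for 1/2 v 0/23 (half of 0.08) and 0.038 for 3/6 v 2/19, both still significant. Its worst-case error is 6.6% at 3 v 22, above chi-square, and 6.0% at 6 v 19, equal to chi-square. It does not repair the problem.

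**The case against.** The strongest reply is that little is lost at the only threshold the plan uses. At 0.05 the worst-case chi-square error is 5.1–7.2%, this is a pilot, and no decision rule depends on these comparisons. That stands as a limit on size. It does not rescue individual p-values: 0.0005 in place of 0.080 misstates the evidence whatever the average error rate.

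A second reply is that the plan does not say its chi-square is uncorrected. This also stands in part, since a Yates correction removes the one-child result. But whether the report shows 0.0005 or 0.11 would then rest on an unstated choice within unnamed software.

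A reader might also infer three stronger claims that the documents do not support:

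- **That both tests fail because the groups are small.** Analysis of variance keeps 5% at these sizes when variances are equal. It is inflated only if the CAV group is more variable, and it turns conservative if that group is less variable. Nothing in the documents indicates which applies.
- **That one patient can produce significance in either age group.** With 6 adult cases, one positive patient gives p = 0.069. With 5 cases it would give 0.041 (1/5 v 0/20; Fisher 0.20), but 6 is the expected count.
- **That the diagnostic accuracy results are affected.** The plan treats the perfusion study against angiography and against wall motion in separate sentences, as paired binary analyses. The CAV versus no-CAV tests read most naturally as comparisons of patient characteristics.

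**Conclusion.** The point holds for the categorical comparisons. At the case counts implied by the plan, chi-square lacks adequate expected cells in every possible 2x2 table. Uncorrected, it can turn a single affected child into p below 0.01 where exact tests give 0.06–0.12. The rise in overall error at 0.05 is modest (at most 7.2%), so the fault lies in misleading individual p-values and not in a general flood of false positives.

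For continuous variables the point is conditional. An error of 11–27% requires a CAV-group SD 1.5–2 times the other group's, which is an assumption. The reason to act is that 2–3 cases cannot show whether the equal-variance assumption is met.

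These conclusions rest on the plan's prevalences, on full recruitment with angiography available for all 25 per group, and, for the one-child result, on no continuity correction. Fewer classifiable patients would make the tables sparser.

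**What to change.** Replace the test sentence in Sample Size & Data Analysis with wording such as:

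> Within each age group, binary variables will be compared between patients with and without CAV by Boschloo's exact test, two-sided, without mid-p adjustment. Continuous variables in adults will be compared by Welch's unequal-variance test. In an age group with fewer than 5 CAV cases, continuous variables will be listed by patient and summarised without a test.

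Ordinary Fisher's exact test is an acceptable alternative to Boschloo's; one of the two should be chosen before data are seen. The cutoff of 5 is a convention and not a derived value, and the sponsor may set another. Some cutoff is needed because Welch's test itself runs at about 12% with 2 cases and 7–8% with 3. On the plan's prevalence, the descriptive route would apply in children with 90% probability.

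The cost is a few sentences, with no change to recruitment or procedures. Some p-values become less favourable, and most pediatric continuous comparisons become descriptive. If Fisher's test is chosen it is conservative, with worst-case error of roughly 1.4–2.0%. Welch's test in adults is not perfect either: with skewed (lognormal) data at 6 v 19 it ran at about 6.9%. The paired accuracy analyses need no change on this account.
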